2.0 Objectives*

2.1 *Describe the purpose, specific aims, or objectives of this research.*

Response: This pilot study will determine the acceptability and potential value of a family-oriented weight management program for individuals receiving anti-psychotic medication for a first episode of psychosis.

2.2 *State the hypotheses to be tested, if applicable.*

NOTE: A hypothesis is a specific, testable prediction about what you expect to happen in your study that corresponds with your above listed objectives.

Response: Patients will lose weight after treatment is initiated in comparison to the two month baseline during which they simply weigh themselves daily.

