Antipsychotic medications also are powerful contributors to weight gain. D'Aurignac, [name], and Dubovsky (2014) demonstrated that olanzapine, but not a placebo, led to a significant weight gain of 3.74 lbs. among healthy participants in only two weeks. Moreover, while not all subjects who received olanzapine gained weight, subjects who gained weight on olanzapine gained an average of 5.28 lbs., and also experienced increases in LDL cholesterol, insulin, and leptin. Among adults with a first-episode psychosis, olanzapine resulted in an increase of 10.34 lbs. in 12 weeks, and increases in insulin, c-peptides and triglycerides (Graham et al, 2005). This increase in weight, as well as increases in cholesterol, leptin, and insulin, continue to increase over the first year of antipsychotics, and then stabilize (Mustafa, et al, 2019; Perez-Iglesias et al, 2014).

There have been numerous studies that have examined weight loss interventions among those with SMI. One of the most well-known, ACHIEVE, compared an 18 month lifestyle intervention (diet and exercise) with a control condition for SMI patients attending day treatment centers. At the end of the 18 months, patients who received the lifestyle intervention had lost 7.5 lbs., in contrast to less than .50 lbs. in the control. Aside from this lengthy and intensive intervention, most studies have not demonstrated this large of an effect. A recent meta-analysis examined 41 randomized clinical trials focusing on interventions that attempted to decrease body weight through improved diet, increased activity, or both (Speyer, et al, 2019). The overall conclusion was that

these interventions led to statistically significant weight loss that was of no clinical significance (a difference of approximately 4.8 lbs), and which did not persist beyond the intervention. While neither this meta-analysis nor an earlier one (Alvarez-Jimenez, Hetrick, Gonzalez-Blanch, Gleeson, & McGorry, 2008) found that the effects were stronger for patients with a shorter duration of disorder, studies of weight management in other samples often find that it is easier to prevent weight gain than to lose weight, given metabolic changes that occur with increased weight. As a result, there has been recent interest in interventions to prevent weight gain among patients experiencing their first episode of SMI.

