While there has been interest in developing effective early interventions for patients experiencing their first episode of a SMI, most of the work has attempted to establish the acceptability and feasibility of interventions (e.g. Thompson, et al, 2020), or has conducted small, uncontrolled studies of changes in weight in a group receiving the intervention. There have been very few randomized clinical trials. For example, Curtis et al (2016) provided 26 patients with a 12 week lifestyle and life skills intervention and 23 patients with standard care. Only 57% completed the programs and were available for analyses. At the end of the 12 weeks, the intervention group, which contained three times as many women as standard care, only gained 4.0 lbs, while the standard care group gained 17 lbs. The largest and most well-controlled study to date was conducted by Alvarez-Jimenez and colleagues (Alvarez-Jimenez et al, 2006; Alvarez-Jimenez et al, 2010). This study randomized 28 patients to a 7-16 session early behavioral treatment including psychoeducation, dietary counseling, exercise, and behavioral therapy and 33 patients to routine care. Patients in the behavioral treatment had gained significantly less weight, 9.0 lbs, by the end of the 3 month program than patients in routine care gain, 15.2 lbs. Nearly 97% of the sample was successfully followed up one year later, and there were not differences in their weight.

Given the poor adherence in one study and the lack of a lasting effect, modifications of these weight management programs would be important to consider. One particular aspect that has been shown to be effective with adolescents is the involvement of a parent.

4.2 Include complete citations or references.

Response: Alvarez-Jimenez, M., Gonzalez-Blanch, C., Vazquez-Barquero, J.L., Perez-Iglesias, R., Martinez-Garcia, O., Perez-Pardal, T., Ramirez-Bonilla, M.L., & Crespo-Facorro, B. (2006). Attenuation of antipsychotic-induced weight gain with early behavioral intervention in drug-naive first-

episode psychosis patients: A randomized controlled trial. *Journal of Clinical Psychiatry*, 67(8), 1253-1260.

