Response: Potential patients and parents in the NAVIGATE program will be identified by the director and clinical staff and will describe the availability of a weight management program designed to help patients maintain a healthy weight

or lose weight. If they are interested, the patient and family member will sign a permission form to provide contact information to the research staff.

10.3 Describe how you will protect the privacy interests of prospective subjects during the recruitment process.

NOTE: Privacy refers to an individual's right to control access to him or herself.

Response: Only patients who indicate an interest in participating will be contacted by the research assistant. All identifying information about participants and parents who are not eligible or who choose not to participate will be deleted.

10.4 Identify any materials that will be used to recruit subjects.

NOTE: Examples include scripts for telephone calls, in person announcements / presentations, email invitations.

 For advertisements, include the final copy of printed advertisements with your submission. When advertisements are taped for broadcast, attach the final audio/video tape. *NOTE: You may submit the wording of the advertisement prior to taping to ensure there will be no IRB-required revisions, provided the IRB also reviews and approves the final version.*

Response: NA

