17.0 Data Management and Analysis*

17.1 Describe the data analysis plan, including any statistical procedures. This section applies to both quantitative and qualitative analysis.

Response: The project is a multiple baseline single case experimental design, with a 2 month baseline data collection. Families will then be randomized to staggered initiation of treatment in blocks of 4 families. We anticipate having 8 participating families at the

beginning of the project and would randomly assign them to start the baseline assessment between 1 and 9 weeks into the project, with the treatment then beginning between weeks 9 and 17. Treatment completion for this initial cohort would be between weeks 21 and 29, and the final follow-up would occur between weeks 29 and 37. Families entering NAVIGATE after the recruitment of the first cohort will be randomly assigned to start the baseline from 1 to 9 weeks after entry. This will provide a significant baseline (2 months) for all participants with different initial points for the study.

Analysis of the daily weights will involve discontinuous growth curve analysis using multi-level modeling (Singer and Willet, 2003). Separate models are developed for each participant which include the daily weights from the baseline (60 days), treatment (90 days) and follow-up (60 days) phases. Given the nature of the data, we would hypothesize significantly different slopes for the baseline vs treatment phases. We would also expect no significant differences between the slopes for the treatment phase and the follow-up phase. The primary analysis involves modeling each individual as a level one variable.

17.2 *If applicable, provide a power analysis.*

NOTE: This may not apply to certain types of studies, including chart/records reviews, survey studies, or observational studies. This question is asked to elicit whether the investigator has an adequate sample size to achieve the study objectives and justify a conclusion.

Response: NA

17.3 *Describe any procedures that will be used for quality control of collected data.*

Response: Data will be reviewed by trained and IRB approved study personnel.

18.0 **Confidentiality***

A. Confidentiality of Study Data

Describe the local procedures for maintenance of confidentiality of study data and any records that will be reviewed for data collection.

A

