22.0 Potential Benefits to Subjects*

22.1 Describe the potential benefits that individual subjects may experience by taking part in the research. Include the probability, magnitude, and duration of the potential benefits. Indicate if there is no direct benefit.

*NOTE: Compensation **cannot** be stated as a benefit.*

Response: Patients who are prescribed antipsychotics often gain significant weight and commonly stop the medication as a result. This can precipitate further psychotic episodes. A program that mitigates the weight gain can improve the health of the patient and the family member (reduced health risks associated with obesity) and reduce the potential for a relapse (which can have multiple social and physical consequences).

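### The only stated analysis of follow-up weights is an expected non-significant difference between treatment and follow-up slopes, which cannot show that the effect lasts

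*Combined protocol and SAP*

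**What the plan says.** Section 17.1 plans a discontinuous growth-curve analysis of daily weights over 60 days of baseline, 90 of treatment and 60 of follow-up. It says "Separate models are developed for each participant which include the daily weights" from all three phases. Two slope comparisons follow. For the first, "we would hypothesize significantly different slopes for the baseline vs treatment phases"; this uses no follow-up weights. For the second, "We would also expect no significant differences between the slopes for the treatment phase and the follow-up phase".

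Nothing else in the protocol analyses follow-up weight. The hypothesis in section 2.2 is "Patients will lose weight after treatment is initiated in comparison to the two month baseline". Section 3.1 names weight as the primary endpoint without a time point. Sections 5.1, 11.1 and 11.2 describe collection only. Section 20.3 compares early withdrawals with completers on treatment response. The power item, 17.2, is answered as not applicable. No margin, confidence interval or end-of-follow-up change is specified.

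On why persistence matters, section 4.1 cites a meta-analysis whose effect was small ("a difference of approximately 4.8 lbs), and which did not persist beyond the intervention"). It then motivates the modified program with "Given the poor adherence in one study and the lack of a lasting effect".

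**The concern.** The follow-up phase is the study's only information on whether an effect outlasts the sessions, and the plan's only stated reading of it is an expected null result. There are two separate difficulties.

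1. **Non-significance is not equality.** With no margin and no planned precision, failing to detect a slope difference may reflect noise alone.
2. **Equal slopes are the wrong target after a loss.** A patient who loses weight in treatment and holds it has a follow-up slope of zero, which differs from the treatment slope. Equal slopes would mean that loss continues at the treatment rate after the sessions stop.

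A patient who did well can therefore count against the stated expectation, and one who deteriorated modestly can count in its favour.

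**Working it through.** There is no planned figure to reproduce, since the documents give no power, margin or variance for this contrast.

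**Step 1: what the contrast measures (no noise assumption).** The inputs are the 90-day treatment and 60-day follow-up phases (17.1) and the 4.8 lb scale (4.1). The 4.8 lb is a between-group difference, used here only as a yardstick.

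Contrast = follow-up slope − treatment slope.

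- Lose 4.8 lb, then hold: 0 − (−4.8/90 × 7) = **0.373 lb/week**.
- Stay flat, then gain 3.2 lb: 3.2/60 × 7 − 0 = **0.373 lb/week**.

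One is full maintenance and the other is deterioration, yet the contrast is identical. More data cannot separate them through this contrast.

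**Step 2: how often the test would mislead (assumptions needed).** Assumed, not in the documents:

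- residual SD 2 lb (range 1–3)
- AR(1) correlation 0.5 or 0.8
- no missing days
- two-sided 0.05
- generalized least squares with known covariance
- either a separate intercept and slope per phase, or a continuous piecewise line

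Standard error of the slope difference at SD 2 lb, in lb/week (it scales with the SD):

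| Model | AR(1) 0.5 | AR(1) 0.8 |
|---|---|---|
| Separate phases | 0.198 | 0.306 |
| Continuous | 0.180 | 0.294 |

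P(flagged) = Φ(d/SE − 1.96) + Φ(−d/SE − 1.96). Example: d = 0.373 and SE = 0.198 give d/SE = 1.885, so P = Φ(−0.075) + Φ(−3.845) ≈ 0.47.

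Probabilities are per participant. Ranges cover both models and both correlations.

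| True course | d, lb/week | Result | SD 1 | SD 2 | SD 3 |
|---|---|---|---|---|---|
| Loses 0.5 lb/week, then flat | 0.500 | flagged | 0.90–1.00 | 0.37–0.79 | 0.19–0.46 |
| Loses 4.8 lb, holds it | 0.373 | flagged | 0.68–0.99 | 0.23–0.55 | 0.13–0.28 |
| Flat, then gains 0.25 lb/week (0.25 × 60/7 = 2.1 lb) | 0.250 | non-significant | 0.21–0.63 | 0.72–0.87 | 0.85–0.92 |
| Loses 4.8 lb, regains 2.4 lb | 0.373 + 0.280 = 0.653 | non-significant | at most 0.01 | 0.05–0.43 | 0.32–0.70 |
| Loses 4.8 lb, regains 4.8 lb | 0.373 + 0.560 = 0.933 | non-significant | below 0.001 | 0.001–0.14 | 0.07–0.47 |

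Full regain after a clear loss is therefore usually detected. The failures are maintained losses that get flagged, and modest regain or gain that passes.

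**Step 3: whether the alternative separates the cases.** The quantity is the modelled change from end of treatment to end of follow-up. At SD 2 lb its 95% CI lies wholly above zero in about 0.02 of simulated runs when a 4.8 lb loss is held, and in 0.74–0.99 when it is fully regained.

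**The case against.** **The plan never says it will read non-significance as durability.** The sentence is an expectation with no decision attached, maintenance is not a named endpoint, and this is a pilot whose only hypothesis compares treatment with baseline. That is correct, and the criticism is conditional on that use. It remains the only stated use of the follow-up weights.

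**In first-episode patients the realistic effect may be slowed gain.** In the two trials described in section 4.1 the intervention arms gained 4.0 and 9.0 lb, against 17 and 15.2 lb in the comparison arms. The protocol also values this outcome. Section 10.2 describes a program "designed to help patients maintain a healthy weight", and section 22.1 says "A program that mitigates the weight gain can improve the health of the patient and the family member". If the effect is a changed slope, asking whether that slope reverts is coherent. This stands: the second difficulty does not apply where gain is merely halted, although section 2.2 does hypothesize loss. The first difficulty applies either way.

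**The needed quantities are already available.** The three-phase model yields a follow-up slope, and if the repeated assessment battery includes weight, there are also clinic weights at end of treatment and final follow-up. True, but the plan does not say to report any of these for maintenance.

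**The probabilities depend on an unstated error model.** This also stands. If independent errors were fitted to autocorrelated weights at SD 2 lb, a held 4.8 lb loss would be flagged roughly 0.7 to 0.8 of the time, and the 2.1 lb gain would be non-significant roughly 0.4 of the time. Step 1 does not depend on this choice.

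**Conclusion.** The concern holds. As the sole stated analysis of follow-up weights, an expected non-significant slope difference cannot support a statement that the effect lasted. Under the weight-loss hypothesis it also targets the wrong quantity. The identical 0.373 lb/week contrast for opposite outcomes rests only on the protocol's phase lengths and the 4.8 lb yardstick. The error rates rest on an assumed SD, autocorrelation and complete daily data, and vary widely with them. They are per participant; no pooled figure is offered, because the documents give no between-patient SD. The flaw is confined to the follow-up question and leaves the baseline-versus-treatment comparison intact. It should be corrected before the data are analysed.

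**What to change.** Replace the follow-up sentence in section 17.1 with wording such as:

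> Maintenance is assessed by the follow-up slope and by the model-based weight change from end of treatment to end of follow-up, each reported with a 95% CI for each participant (and on average if a multilevel model across participants is fitted). A non-significant difference between treatment and follow-up slopes is not taken as evidence of maintenance.

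Also report the treatment-phase slope with its 95% CI beside the baseline-versus-treatment contrast, so that loss can be told from slowed gain.

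Optionally, if the investigators wish to call weight maintained, they should state a regain margin before data review and require the upper confidence limit to lie below it. Otherwise they report the estimate and interval only.

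**Cost.** This is a little more reporting from the same data and model; an average across participants needs a model fitted across participants. Maintenance also becomes harder to claim. At SD 2 lb the 95% CI half-width for the change is about 2.2–3.5 lb per participant (SD 1: 1.1–1.8; SD 3: 3.2–5.3). A truly stable participant would have an 80% chance of meeting a margin only if it were about 3.1–5.1 lb (SD 1: 1.5–2.5; SD 3: 4.6–7.6). That is comparable to the 4.8 lb yardstick, so for single participants the estimate and interval may be all that is useful.

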18.2 A. How long will the data be stored?

Response: IRB correspondence will be maintained for three years after the closure of the study. The Master ID list will be deleted as soon as all of the participants have completed final data collection. The working data files will be stored for three years after the completion of the study or the publication of the results, whichever is later.

18.3 A. Who will have access to the data?

Response: Drs. [name], [name], and [name] will have access to the data. A graduate student with statistical qualifications will also have access to the data for analysis.

18.4 A. Who is responsible for receipt or transmission of the data?

Response: A research assistant will collect the self report data and store it in UB BOX. The daily weight data will be collected by an app and uploaded to UB BOX.

18.5 A. How will the data be transported?

Response: Paper data will be transported by [name] to his office. Electronic data will be uploaded from password protected computer at the clinic to UB BOX.

B. Confidentiality of Study Specimens

Describe the local procedures for maintenance of confidentiality of study specimens.

N/A: No specimens will be collected or analyzed in this research.
(*Skip to Section 21.0*)

18.6 B. Where and how will all specimens be stored? Include information about: physical controls, authorization of access, and labeling of specimens, as applicable.

Response:

18.7 *B. How long will the specimens be stored?*

Response:

18.8 *B. Who will have access to the specimens?*

Response:

18.9 *B. Who is responsible for receipt or transmission of the specimens?*

Response:

18.10 *B. How will the specimens be transported?*

Response:

19.0 Provisions to Monitor the Data to Ensure the Safety of Subjects*

- N/A:** This study is not enrolling subjects, or is limited to records review procedures only. This section does not apply.

NOTE: *Minimal risk studies may be required to monitor subject safety if the research procedures include procedures that present unique risks to subjects that require monitoring. Some examples include: exercising to exertion, or instruments that elicit suicidality or substance abuse behavior. In such cases, N/A is not an acceptable response.*

19.1 *Describe the plan to periodically evaluate the data collected regarding both harms and benefits to determine whether subjects remain safe.*

Response: Participants in this study continue with their regular psychiatric appointments along with this additional intervention. Assessing the weight of patients on antipsychotic medications is part of the treatment guidelines for patients on these medications.

19.2 *Describe what data are reviewed, including safety data, untoward events, and efficacy data.*

Response: Weights will be monitored weekly by the case manager.

19.3 *Describe any safety endpoints.*

Response: NA

19.4 *Describe how the safety information will be collected (e.g., with case report forms, at study visits, by telephone calls with participants).*

Response: NA

19.5 *Describe the frequency of safety data collection.*

Response: NA

19.6 *Describe who will review the safety data.*

Response: See section 20.2.

19.7 *Describe the frequency or periodicity of review of cumulative safety data.*

Response: NA

19.8 *Describe the statistical tests for analyzing the safety data to determine whether harm is occurring.*

Response: NA

19.9 *Describe any conditions that trigger an immediate suspension of the research.*

Response: NA

20.0 **Withdrawal of Subjects***

N/A: This study is not enrolling subjects. This section does not apply.

20.1 *Describe anticipated circumstances under which subjects may be withdrawn from the research without their consent.*

Response: Participants who leave the NAVIGATE program or experience a psychotic relapse requiring hospitalization longer than one week will be removed from the study. Parents or support participants of the withdrawn participant may continue the study.

20.2 *Describe any procedures for orderly termination.*

NOTE: Examples may include return of study drug, exit interview with clinician. Include whether additional follow up is recommended for safety reasons for physical or emotional health.

Response: A final phone call with the participant and/or family member will take place. Arrangements to collect the Bluetooth scale will be made.

20.3 Describe procedures that will be followed when subjects withdraw from the research, including retention of already collected data, and partial withdrawal from procedures with continued data collection, as applicable.

Response: No further treatment or assessments will be conducted on the withdrawn participant. However, any participant that is still willing to participate can continue the study. Data will be maintained for participants who remain in the study through 50% of the weight intervention program. Data for participants who withdraw sooner will also be retained for comparison to those who complete the intervention with respect to response to treatment.

